4.2.2 Major protocol deviation

If a patient who was randomized to routine physiotherapy alone received cycling, this was considered a major protocol deviation.

4.3 Analysis populations

We will include all eligible randomized patients (i.e., excluding post-randomization exclusions representing non-eligible patients), according to the treatment they were randomized to receive. The analyses of our primary outcome will only include patients who survived to 3 days post-ICU discharge, as specified in our original protocol and sample size calculation.[21] The analysis of the PFIT-s at other timepoints (ICU awakening, ICU discharge, and hospital discharge) and all performance-based (strength and function) and patient-reported (e.g., quality-of-life) outcomes will only include patients who survive to the given timepoint. The analysis of hospital discharge location will only include those discharged from the hospital alive. The analysis of ICU and hospital mortality and length of stay, as well as duration of mechanical ventilation, will include all enrolled patients.

5.0 TRIAL POPULATION

5.1 Screening data

We will report the total number of patients screened (i.e., meeting all inclusion criteria), and those with exclusion criteria based on screening logs from participating sites. For eligible patients, we will report reasons for non-enrollment.

5.2 Eligibility

Table 1 outlines trial inclusion and exclusion criteria.[21]

5.3 Recruitment

We will report the CONSORT diagram for all participants throughout the study (Figure 1).

5.4 Withdrawal/ follow-up

We will document patient withdrawals and losses to follow-up in our CONSORT diagram.

5.5 Baseline patient characteristics

We will summarize categorical data as counts and percentages. We will summarize continuous data as means, standard deviations, or median and interquartile range, if data are non-normally distributed. We will not conduct tests of statistical significance between randomized groups; rather, we will note the clinical importance of any imbalance between groups.

5.6 Consent and randomization

Informed consent and randomization procedures have been previously described in our protocol [21]. Briefly, research coordinators screened the participating ICUs for potentially eligible patients, identified eligible patients, and sought *a priori* consent from the patient, their substitute decision-maker or legally authorized representative.

6.0 ANALYSIS

6.1 Outcome definitions

Tables 2 and 3 describe our primary and secondary outcomes, measurement time points, and analysis methods.

Outcomes

Primary Outcome

The primary outcome is the PFIT-s measured at 3 days post-ICU discharge.[14, 15] The PFIT-s includes 4 items (arm strength, leg strength, ability to stand, and step cadence), each scored from 0 to 3, summed to a maximum of 12 points, and transformed to a total score of 10 (Table 4).[14] Higher scores represent better function. It was developed in an ICU population, includes functional items, and, unlike the 6-minute walk test (6MWT), can be measured serially over time (as few patients can walk at ICU awakening).[22] We chose the PFIT-s because we expect all

ICU patients will be able to complete part of the assessment even if they cannot stand (e.g., arm or leg strength), limiting floor effects. The PFIT-s is reliable and valid, with strong psychometric properties (reliability range = 0.996 to 1.00 [15]; convergent validity with the 6MWT and muscle strength [14]). We selected 3 days post-ICU discharge because it is proximal to the intervention and prior studies documented variable delivery of rehabilitation post-ICU[23] that may contaminate later evaluations.

Secondary Outcomes

Secondary outcomes include performance-based, patient-reported, and those collected by chart review. Performance-based measures included muscle strength (Medical Research Council Sum Score)[24, 25] and function (30-second sit to stand,[26, 27] 2-minute walk test).[28] The 30-second sit-to-stand and 2-minute walk test have age- and sex- based reference values, and good reliability in critically ill or frail elderly populations.[27, 28] Patient-reported measures included the Patient-Reported Functional Scale for the ICU (PRFS-ICU),[29, 30] critical care-related psychological distress using the Intensive Care Psychological Assessment Tool (IPAT),[31, 32] health-related quality-of-life using the EuroQol (EQ-5D-5L™),[33-35] and the Hospital Anxiety and Depression Scale (HADS).[36] We also collected frailty (Clinical Frailty Scale),[37] Katz activities of daily living (ADL) scale,[38] duration of mechanical ventilation, length of stay (ICU and hospital), mortality (ICU, hospital, 90-day post-randomization), and change in living location at hospital discharge from baseline. Due to funding limitations, we restricted 90-day post-randomization outcomes to those enrolled after March 7, 2018.

Adverse Events

We will report the following adverse events if they occurred during or immediately after in-bed cycling or routine physiotherapy interventions, if they were attributable by the clinical team to the randomized intervention, and resulted in a clinical deterioration of the patient's status [3, 7, 39-41]:

Severe adverse events: unplanned extubation, cardiac arrest, or fall to knees during routine PT/ rehabilitation activities.

Serious adverse events: Concern for myocardial ischemia or suspected new unstable/ uncontrolled arrhythmia; Sustained symptomatic bradycardia (<40 bpm) or tachycardia (>140 bpm) and clinical deterioration attributed to in-bed cycling or routine PT/ rehabilitation activities; Sustained hypertension (mean arterial pressure >120 mmHg) and clinical deterioration attributed to in-bed cycling or routine PT/ rehabilitation activities; Sustained O₂ desaturation below baseline and clinical deterioration attributed to in-bed cycling or routine PT/ rehabilitation activities; Marked ventilator dyssynchrony; Bleeding at femoral catheter site attributed to in-bed cycling or routine PT/ rehabilitation activities; New bruising at femoral catheter site attributed to in-bed cycling or routine PT/ rehabilitation activities.

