3.0 STUDY METHODS

3.1 Trial design

CYCLE (Critical care cycling to improve lower extremity strength) is a 360-patient, international, multi-center, open-label, parallel group randomized trial (1:1 ratio) with blinded primary outcome assessment at 3 days post ICU discharge. Assessors were blinded to treatment group allocation.

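### SAP 6.1 requires attribution and clinical deterioration for every adverse event, but the listed items do not, and 6.5 plans no count by group without that filter

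*SAP*

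**What the plan says.** SAP 6.1 (Adverse Events) opens with a sentence that governs the whole list. Events are reported "if they occurred during or immediately after in-bed cycling or routine physiotherapy interventions", and further "if they were attributable by the clinical team to the randomized intervention, and resulted in a clinical deterioration". The conditions are cumulative.

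The list then names three severe events, "unplanned extubation, cardiac arrest, or fall to knees during routine PT/ rehabilitation activities", with no attribution or deterioration wording of their own. Among the serious events, the heart-rate, hypertension and desaturation items each add "and clinical deterioration attributed to in-bed cycling or routine PT/ rehabilitation activities". The bruising item reads "New bruising at femoral catheter site attributed to in-bed cycling or routine PT/ rehabilitation activities", which is attribution without deterioration.

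Section 3.1 describes the trial as "open-label, parallel group randomized trial (1:1 ratio) with blinded primary outcome assessment at 3 days post ICU discharge" and names only the assessors as blinded. Section 6.5 reports severe and serious events by group, per patient and per randomized-intervention day, restricted to days on which the intervention was given. It plans no statistical test and no count of listed events that disregards attribution or deterioration.

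**The concern.** There are two problems.

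First, the lead-in and the list cannot both be taken at face value. If the lead-in governs, the extra wording on some items is redundant, and a fall or a new bruise without deterioration is not an event. If each item's own wording governs, that same fall or bruise counts. Two analysts could produce different harm tables from the same data.

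Second, attribution is a judgement by the clinical team. In an open-label trial with only assessors described as blinded, that team presumably knows the arm. If staff are readier, or less ready, to blame cycling than familiar physiotherapy, the comparison by group partly reflects that readiness. Without the unfiltered count, a reader cannot see how many listed events were removed or whether removal differed by arm. By contrast, the SAP protects judgement on the primary outcome: under Supplement 2, incomplete PFIT-s items are scored by people blinded to allocation and site.

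**Working it through.** The SAP gives no harm rate to reproduce, so the main check compares texts.

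**Step 1. Conditions in each item's own wording (6.1), against a lead-in that demands both for all.**

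| Item | Class | Attribution | Deterioration |
|---|---|---|---|
| Unplanned extubation | severe | no | no |
| Cardiac arrest | severe | no | no |
| Fall to knees | severe | no | no |
| Ischaemia or unstable arrhythmia | serious | no | no |
| Bradycardia or tachycardia | serious | yes | yes |
| Hypertension | serious | yes | yes |
| Desaturation | serious | yes | yes |
| Ventilator dyssynchrony | serious | no | no |
| Femoral site bleeding | serious | yes | no |
| Femoral site bruising | serious | yes | no |

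Ten items: 3 carry both conditions, 2 attribution only, 5 neither. The lead-in therefore adds a deterioration condition to 2 + 5 = 7 items and an attribution condition to 5.

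**Step 2. Where the added conditions matter.** Cardiac arrest would normally count as deterioration, so that condition removes little there; attribution still could. The deterioration condition matters mainly for falls, extubations, bleeding and bruising.

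**Step 3. What the filter could do to the comparison (all rates assumed).** For one arm:

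reported events = N × true rate × P(deterioration) × P(attributed in that arm)

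N = 360 / 2 = 180 per arm (SAP 3.1). Assume the same true rate of listed events around sessions in both arms (2% to 10% of patients, or 3.6 to 18.0 patients per arm) and the same deterioration share (25% to 75%). The reported ratio, Cycling to Routine, then equals the ratio of the attribution probabilities:

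| Attribution, Cycling / Routine | Reported ratio | If reversed |
|---|---|---|
| 50% / 50% | 1.0 | 1.0 |
| 60% / 40% | 1.5 | 0.67 |
| 80% / 40% | 2.0 | 0.5 |
| 90% / 30% | 3.0 | 0.33 |

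Example at a 5% true rate and 50% deterioration: 180 × 0.05 = 9.0 true events per arm. Reported: 9.0 × 0.5 × 0.8 = 3.6 in Cycling and 9.0 × 0.5 × 0.4 = 1.8 in Routine.

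With equal attribution of 50% the ratio is undistorted, but the share of events lost is 1 − 0.5 × P(deterioration): 1 − 0.5 × 0.75 = 62.5% to 1 − 0.5 × 0.25 = 87.5%.

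These figures show the mechanism only. None of the rates comes from the SAP.

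**The case against.** Attribution is a defensible way to separate therapy-related events from the background of critical illness. Arrhythmia and dyssynchrony occur in ventilated patients whether or not therapy is given. A count by timing alone would collect such background events and might collect more of them in the Cycling arm, where 30 minutes a day of cycling is added to routine physiotherapy (SAP 3.2). The denominators in 6.5 are patients and days, so they would not correct for longer session time. Concern for ischaemia, suspected arrhythmia and marked dyssynchrony also remain judgements by the same staff, and five items keep attribution in their own wording. An item-level count therefore reduces the dependence on open-label judgement without removing it. All of this stands, and it is why the item-level count should not replace the filtered one.

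It can also be said that the items merely repeat a general rule. Redundancy could explain the three items that repeat both conditions, but it does not tell an analyst whether a bruise without deterioration counts.

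The protocol, not shown here, may describe event capture or adjudication, so the SAP's silence does not show that there is none. Supplement Table 1 labels the collected events as study-related, so unattributed events may not have been recorded. That limits the remedy.

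A reader might infer that the plan discards falls, extubations and bruises altogether. It discards only those that fail a condition. A reader might also infer that the harm comparison is biased for or against cycling. The SAP does not support either direction: the illustrated ratio moves above or below 1 with the assumed attribution pattern, and the expected counts in the example differ by fewer than two events.

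**Conclusion.** The point holds as an inconsistency in the event definition and a gap in harm reporting. Read literally, listed events without deterioration, or not attributed by clinical staff, are not reported, and 6.5 shows no unfiltered count by group. That these staff know the arm is inferred from the open-label design; the SAP does not say it in words.

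The size and direction of any bias between arms cannot be determined from the document. The consequence is also bounded. The harms analysis is descriptive, the primary analysis is untouched, and ICU and hospital mortality are analysed in all enrolled patients (SAP 4.3), so death does not pass through this filter. It would be too strong to conclude that the safety comparison is invalid or that a timing-only count should become the main result.

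**What to change.** In 6.1, reconcile the lead-in with the list: keep the timing condition in the lead-in, and let each item carry only the further conditions in its own definition.

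In 6.5, report by arm, side by side:

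- (a) the listed events around a session under their item definitions;
- (b) the subset attributed by the clinical team and causing deterioration.

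Neither should stand as the sole safety result. Add a note that (a) includes background events and that session time may be longer in the Cycling arm.

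If the case report form captured only attributed events, (a) cannot be built for the items without their own attribution wording. The table should then be labelled as events attributed by clinical staff in an open-label trial.

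The cost is revised wording and one extra column. The downside is somewhat higher and less specific counts.

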6.2 Analysis methods

Statistical analysis

We will analyze patients according to the group to which they were randomized for all outcomes and will use multiple imputation to handle missing data (see section 6.3). We will summarize

baseline characteristics by group reported as mean (SD) or median (first quartile, third quartile) for continuous variables and count (percent) for categorical variables. The criterion for statistical significance will be set at $\alpha=0.05$ for the Primary Outcome. P-values will be reported to 3 decimal places, with those less than 0.001 reported as $p<0.001$.

Analysis of the Primary outcome

To determine if there is a difference in PFIT-s score at 3 days after ICU discharge between the Cycling and Routine groups, we will conduct a linear regression, including randomization (Cycling vs. Routine) as an independent variable. We will adjust for age (≥ 65 years versus <65 years) and clinical site as these were used as stratification variables in the randomization. We will report the results of the regression as mean difference in PFIT-s with corresponding 95% confidence intervals (CIs) and p-values. We consider a 1-point difference in score clinically important.[14, 16] Although the goal was to have all outcome assessors remain blinded to treatment allocation, this was not always feasible. To maximize use of available data, we will include all PFIT-s measures at 3 days post-randomization, regardless of blinding status of the outcomes assessor and report the proportion of assessments performed by blinded assessors.

To account for incomplete component data in the PFIT-s at 3 days post-ICU, we will concurrently consider data from the PFIT-s, 30s sit-to-stand, and 2-minute walk tests. We will evaluate all PFIT-s data components at 3-days post-ICU. We will identify all patients with any incomplete physical function data and review the scored values for all 4 components of the PFIT-s (i.e., shoulder flexion, knee extension, level of assistance required for the sit-to-stand, and step cadence). In the PFIT-s, a score of “0” represents a lack of physical ability to complete the outcome measure. Thus, if a patient attempted the item and was unsuccessful, the item receives a score of “0”, which is a true 0 (Table 4). See supplementary appendix for further details. Table 2 describes the primary outcome analysis.

Analysis of Secondary outcomes

For each continuous secondary outcome, we will conduct a linear regression. We will conduct secondary outcome analyses adjusting for age (≥ 65 years versus <65 years) only. To avoid the risk of overfitting in our analyses, we will not adjust for center when analysing our secondary outcomes. We will report the results of the linear regressions as mean differences with corresponding 95% CIs. If needed to normalize the data, we will perform the linear regression on the log-transformed outcome. If the data are still skewed, we will perform nonparametric analyses. Because secondary analyses are underpowered and hypothesis-generating, we will not present p-values. In the Supplementary appendix, we describe the scoring algorithm to account for incomplete data in the 30 Second Sit to Stand and 2-minute walk tests based on a patient’s observed function.

Time to ICU, hospital, and 90-day mortality will be analyzed using Cox proportional hazards regression analysis. We will report hazard ratios (HRs) and corresponding 95% CIs. All other binary outcomes will be analyzed using logistic regression analysis, reporting odds ratios (ORs) with corresponding 95% CIs. We will check the assumptions of the different regression analyses by examining residuals and using other relevant methods. Table 3 describes secondary outcomes analyses. Analysis of Harms is described in Section 6.5.

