3.2 Randomization

Randomization occurred after informed consent was obtained. We concealed allocation and used a central randomization process. We used a web-based, secure randomization service (<http://www.randomize.net/>). After informed consent, the site research coordinator logged in to the website, registered the patient, and received the randomized assignment, ensuring allocation concealment. Patients were stratified by center and age (≥ 65 vs. < 65 years old).

Interventions and comparator

Intervention (Cycling): Patients were randomized to receive 30 minutes/ day of in-bed cycling in addition to routine physiotherapy interventions, 5 days per week, during their ICU stay. Cycling occurred for a maximum of 28 days or stopped when the patient could march on the spot for 2 consecutive days, whichever occurred first.

Comparator (Routine): Patients received routine physiotherapy interventions per current institutional practice. Routine PT included, based on the patient's alertness and medical stability, activities to maintain or increase limb range of motion and strength, in- and out-of-bed mobility, ambulation, and assistance with optimizing airway clearance and respiratory function.[4, 10-12]

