3.3 Sample size

Sample size and power

Our sample size of 360 patients was based on identifying a 1.0 point mean difference[13] between the Cycling and Routine groups for the Physical Function Test for ICU-scored (PFIT-s) measured at 3 days after ICU discharge.[14, 15] Psychometric studies of the PFIT-s identified the minimal clinically important difference was 1.0 points.[14, 16] Logistic regression analysis of patients enrolled in TryCYCLE [7] and the CYCLE pilot randomized study [8] identified that each 1.0 point increase in PFIT-s at ICU discharge (representing better function) was associated with a 40% reduction in the composite outcome of death, readmission to ICU, or requiring paid assistance for activities of daily living at hospital discharge.[13] Based on a standard deviation of 2.5 points at ICU discharge,[7, 17] a 1.0 point difference between groups,[13, 14, 16] and 90% power (0.05 alpha), we need to randomize and analyze 266 patients (133 per group). Based on 66 patients enrolled in the CYCLE Pilot RCT, we anticipated approximately 35% total attrition (25% ICU mortality, 1% mortality in the first 3 days post-ICU discharge, 5% missed primary outcome assessments at 3 days post-ICU, and 5% unblinded). Therefore, we will recruit 360 patients overall.

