6.3 Missing data

To account for missing data in our performance-based and patient-reported outcomes, we will use multiple imputation for our analyses.[42-44] In the Cox proportional hazards analyses for ICU and hospital mortality outcomes, patients with incomplete follow-up will be censored at the time of last contact.

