30 second sit to stand test [26, 50]	Patient completes as many full sit to stand repetitions as possible within 30 seconds. Higher scores represent better strength.	ICU awakening, ICU discharge, 3 days after ICU discharge, hospital discharge	Includes survivors at each time point. Separate linear regressions for each timepoint, adjusted for age
2-minute walk test [28, 51]	Patient walks as far as possible over 2 minutes. Higher scores represent better endurance.	ICU discharge, 3 days after ICU discharge, hospital discharge	Includes survivors at each time point. Separate linear regressions for each timepoint, adjusted for age

Outcome	Description of Outcome	Measurement Timing	Analysis
Intensive Care Psychological Assessment [31]	Patients answer 10 questions related to psychological distress in the ICU using a 3-point scale (0=no; 1=yes, a bit; 2=yes, a lot), summed to a total score. Total scores range from 0 to 20, with higher scores representing more distress.	Following ICU awakening assessment	Includes survivors. Linear regression, adjusted for age
Patient-reported functional score for ICU [52]	Patients answer 6 questions about their current perception of function, using an 11-point scale (0=unable to perform activity; 10=able to perform activity at same level as before ICU admission), summed to a total score. Total scores range from 0 to 60, with higher scores representing better function.	ICU discharge, hospital discharge, 90-days post-randomization	Includes survivors at each time point. Separate linear regressions for each timepoint, adjusted for age
Euro-QOL 5D 5L Index [35]	Patients answer 5 questions about their current perception of mobility, self care, usual activities, pain/discomfort, and anxiety/depression, scored according to a prescribed algorithm. Higher scores represent better perceptions of health.	ICU discharge, hospital discharge, 90 days post-randomization	Includes survivors at each time point. Separate linear regressions for each timepoint, adjusted for age
Euro-QOL Visual Analogue Scale [35]	Patients rate their overall health on a 100-point visual analogue scale (0= worst health; 100= best health).	ICU discharge, hospital discharge, 90 days post-randomization	Includes survivors at each time point. Separate linear regressions for each timepoint, adjusted for age

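### Overfitting does not justify dropping centre, a randomisation stratum, from continuous secondary models that hold at least as many patients as the primary (minor)

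*SAP*

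**What the plan says.** SAP 3.2: "Patients were stratified by center and age". For the primary outcome, 6.2 adjusts the linear regression for age group and "clinical site as these were used as stratification variables in the randomization". The subgroup models in 6.4 keep age and centre and add an interaction. Sensitivity analyses ii to iv keep them in subsets of the primary population (blinded assessments, adherent patients, complete cases).

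For every secondary outcome 6.2 adjusts for age only, and gives one reason: "To avoid the risk of overfitting in our analyses, we will not adjust for center when analysing our secondary outcomes". Table 3 follows, for example "Separate linear regressions for each timepoint, adjusted for age".

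On who is analysed, 4.3 restricts performance and patient-reported outcomes to survivors at each timepoint. It states that ICU and hospital length of stay, "as well as duration of mechanical ventilation, will include all enrolled patients". Section 6.3 adds: "To account for missing data in our performance-based and patient-reported outcomes, we will use multiple imputation for our analyses".

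Sensitivity analysis v (6.4 and Table 2) repeats the primary regression without site. Its objective asks whether centre affects the cycling effect. Its Table 2 hypothesis is that dropping site leaves the estimate unchanged.

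**The concern.** Overfitting depends on how many parameters a model carries for the information it has. The SAP accepts age plus site for PFIT-s at 3 days, and for models that are more demanding than that one. It then calls the same adjustment a risk for linear models fitted to the same survivors, or to more patients. The reason cannot hold for both.

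What is at stake is precision. If centres differ in outcome level, a model without centre leaves that variation in its error term although randomisation was stratified on it. The interval is then wider than the design warrants. Section 6.2 reports these outcomes without p-values, so the interval is the only inference shown.

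Sensitivity analysis v raises a smaller matter. Comparing two estimates of one average effect does not show whether the effect varies between centres, so the stated objective asks more than the analysis can answer.

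**Working it through.** **Plan's own figure.** Section 3.3 uses a difference of 1.0, SD 2.5, 90% power and two-sided 5%. The normal approximation gives 2 × (1.960 + 1.282)² × 2.5² / 1.0² = 131.4, so 132 per group. The noncentral t gives 133 per group, 266 in total, as stated.

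**Expected sizes.** The rates in 3.3 are "25% ICU mortality, 1% mortality in the first 3 days post-ICU discharge".
- Alive at 3 days post-ICU: 360 × (1 − 0.25 − 0.01) = 266.4, about 266. That this equals the required 266 is a coincidence.
- ICU survivors: 360 × 0.75 = 270.
- Length of stay and ventilation duration: all enrolled, 360 planned.

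The further 5% missed and 5% unblinded in 3.3 are not subtracted. Missing outcomes are imputed (6.3), and for the primary 6.2 keeps assessments "regardless of blinding status of the outcomes assessor".

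**Which outcomes qualify (at least 266, linear or log-linear).**
- At 3 days: MRC sum score, 30-second sit-to-stand, 2-minute walk.
- At ICU discharge: PFIT-s, MRC sum score, sit-to-stand, walk, PRFS-ICU, EQ-5D index, EQ-5D visual analogue scale, Katz.
- All enrolled: ICU and hospital length of stay, ventilation duration.

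**Parameter count.** With K centres as fixed effects the model has K + 2 parameters (intercept, treatment, age, K − 1 centre terms). The SAP does not give K; 10, 16 and 25 are assumed.

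| Centres | Parameters | Patients per parameter, n = 266 | n = 360 |
|---|---|---|---|
| 10 | 12 | 22.2 | 30.0 |
| 16 | 18 | 14.8 | 20.0 |
| 25 | 27 | 9.9 | 13.3 |

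The n = 266 column is also the primary model's own position.

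**Cost or gain in interval width.** Simulation: 360 randomised, survival 0.74, SD 2.5, effect 1.0, unequal centres, blocks of 4 within centre and age, Normal errors, 2,000 trials per scenario. Block size, centre number and ICC are assumptions.

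| ICC | Age-only / fixed centre: 10, 16, 25 centres | Mean width at 16 centres: age-only / fixed / random intercept | Age-only / random, 16 centres |
|---|---|---|---|
| 0 | 0.994, 0.989, 0.980 | 1.208 / 1.222 / 1.204 | 1.003 |
| 0.02 | 1.003, 0.998, 0.990 | 1.208 / 1.211 / 1.198 | 1.008 |
| 0.05 | 1.016, 1.013, 1.004 | 1.205 / 1.190 / 1.180 | 1.021 |
| 0.10 | 1.040, 1.038, 1.030 | 1.203 / 1.159 / 1.151 | 1.045 |
| 0.20 | 1.095, 1.097, 1.087 | 1.197 / 1.091 / 1.087 | 1.101 |

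Age-only coverage was 0.946 to 0.969, and the mean estimate 0.98 to 1.01 for a true 1.0.

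*Hand check, 16 centres.* Removing the between-centre variance shortens the interval by a factor of about √(1 − ICC), so the ratio is roughly 0.989 (its value at ICC 0) divided by √(1 − ICC). This gives 0.989/√0.95 = 1.015, 0.989/√0.90 = 1.042 and 0.989/√0.80 = 1.106, against simulated 1.013, 1.038 and 1.097.

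A separate simulation with 10, 17 and 30 centres of similar size and no treatment effect agreed. At n = 266 the widths with and without centre were 1.21-1.22 and 1.20-1.21 at ICC 0, 1.15-1.16 and 1.20 at 0.10, and 1.08-1.09 and 1.20 at 0.20.

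**Zero-heavy outcomes.** Sit-to-stand and walk may contain many zeros under the Supplement 3 scoring. With 35% zeros assumed, the age-only / fixed ratios over 10 to 25 centres were 0.980-0.994 (ICC 0), 1.000-1.013 (0.05), 1.021-1.032 (0.10) and 1.070-1.079 (0.20).

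**Where the SAP's reason can hold.** About 360 × 0.25 = 90 ICU deaths are expected. A Cox model with treatment, age and centre terms (K + 1 parameters) has 90/11 = 8.2 events per parameter at 10 centres and 90/21 = 4.3 at 20.

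**The case against.** The choice is prespecified, and 6.2 and Table 3 agree with each other. The SAP calls these outcomes underpowered and hypothesis-generating. One covariate set across linear, logistic and Cox secondaries is a defensible aim, and the loss is unproven because the SAP gives neither centre number nor ICC. Against fixed effects even the sign is open at low ICC: from 2% narrower to 1.6% wider between 0 and 0.05. All of this stands, and it is why the point is minor. But uniformity is not the reason the SAP gives.

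Equal size is only nominal for sit-to-stand and walk. Table S3 leaves many of their cells missing, and imputed patients carry less information than observed ones. If only 50-70% were observed (an assumption), n would be 133 to 186. With 16 to 25 centres the age-only interval would then be 2-7% narrower than with fixed centre effects at ICC 0, and 0-5% narrower at 0.05. This also stands. It argues for a random intercept over fixed effects, and it makes the 3-day MRC sum score the clearest case.

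Length of stay and ventilation duration are skewed, so the widths above only illustrate those outcomes, and the nonparametric fallback in 6.2 may apply instead.

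A reader might infer that omitting a stratification factor biases these estimates or makes the intervals too short. In these linear models it does neither: age-only coverage stays at about 95-97%. A reader might also extend the criticism to every secondary. The logistic and Cox models, and the 90-day outcomes restricted by enrolment date (6.1), can have sparse information, and the SAP's reason is plausible there.

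Nor is sensitivity analysis v contradictory in what will be done. Section 6.4 introduces all five analyses as robustness checks, and the Table 2 hypothesis and analysis match. Only the objective is loosely worded.

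**Conclusion.** The concern holds within limits. The overfitting reason is too broad: it does not fit continuous secondaries analysed by linear or log-linear regression at 3 days post-ICU, at ICU discharge, or in all enrolled patients. That inconsistency follows from the SAP's own text and rates, and does not depend on the number of centres.

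The consequence does depend on it. With 10 to 25 centres and Normal errors assumed, the loss of precision is negligible to small unless centres differ materially, reaching 9-10% of interval width only at an ICC of 0.20. Validity is not affected. Severity is minor. The sensitivity analysis v point is one of wording only.

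**What to change.** In 6.2 and Table 3, state one rule: continuous secondaries analysed by linear or log-linear regression at ICU discharge, at 3 days post-ICU, or in all enrolled patients are adjusted for age (fixed effect) and centre (a single random intercept). No pooling of small centres is then needed. Ventilation duration has no row in Table 3 as available to me, so the rule in 6.2 should name it.

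Confine the overfitting sentence to the logistic, Cox and smaller outcomes (such as the 90-day ones), which stay age-only. The SAP gives no expected numbers for ICU awakening or hospital discharge. Those outcomes can stay age-only too, but the text should say so, so that no model is left undefined. The nonparametric fallback stays as planned.

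In 6.4 and Table 2, restate the objective of sensitivity analysis v as robustness of the estimate to omitting centre.

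Cost: wording changes and one model term, with no new data. The secondary family no longer shares one covariate set. The gain is negligible if centres do not differ, but in the simulation the random intercept then cost about 0% in interval width.
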